For the final report, pregnancies exposed to nemolizumab and their matched comparators will be identified in the selected databases. The final report analyses will employ a target trial emulation approach using a sequential matched cohort design that aligns cohort entry by gestational week (Caniglia et al., 2023; Hernández-Díaz et al., 2023). Nemolizumab-exposed pregnancies will be 1:4 matched to comparator pregnancies based on maternal age at cohort entry, gestational week of dispensing, indication, and calendar week. The frequency of pregnancy and infant outcomes among nemolizumab-exposed pregnancies and comparator pregnancies will be calculated. In the comparative analysis, pregnancies among patients with moderate to severe AD or PN who were

exposed to nemolizumab will be contrasted with the comparator groups using stabilized inverse probability of treatment weighting (IPTW) to adjust for potential confounding. RRs will be estimated using robust Poisson regression models and HRs using Cox proportional hazards models.

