7.3.3 Exclusion Criteria

7.3.3.1 JAK Inhibitors

Pregnancies among women exposed to oral JAK inhibitors indicated for moderate to severe AD or PN (i.e., abrocitinib, upadacitinib, baracitinib) from 5 half-lives (specific for each medication) prior to ECD through the end of pregnancy will be excluded because they are contraindicated

during pregnancy. This list may be updated if other JAK inhibitors are approved for moderate to severe AD or PN during the study period.

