7.3.4 Identification of Moderate to Severe AD

Women will be considered to have moderate to severe AD if they meet one of the following criteria between 12 months prior to ECD and the end of pregnancy:

1. ≥ 2 claims with an AD diagnosis code (ICD-10-CM: L20*), at least 30 days apart, from any physician and ≥ 1 dispensing of nemolizumab, dupilumab, abrocitinib, upadacitinib, baricitinib, tralokinumab, or lebrikizumab; OR
2. ≥ 2 claims with an AD diagnosis code, at least 30 days apart, from any physician and ≥ 2 dispensings on different days of high potency topical corticosteroids or systemic immunosuppressants; OR
3. ≥ 2 claims with an AD diagnosis code, at least 30 days apart, from a dermatologist or allergist and ≥ 3 dispensings on different days of medium potency topical corticosteroids, topical tacrolimus, phototherapy, or oral/parenteral corticosteroids.

In a validation study, a similar algorithm had a positive predictive value (PPV) of 76% (95% confidence interval [CI] 53%, 90%; [Chomistek et al., 2023a](#)). Nemolizumab, abrocitinib, upadacitinib, baricitinib, tralokinumab, and lebrikizumab were not included in the validation study because they were not approved for moderate to severe AD at the time of algorithm development. A full list of diagnosis codes and drugs included in this algorithm can be found in [Appendix C](#).

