7.3.6.5 Unexposed Cohort

The Unexposed Cohort will include all pregnancies among women with moderate to severe AD or PN who have no dispensings or administrations of nemolizumab or the other monoclonal antibody treatments used to defined the Other AD/PN Treatment Cohort (i.e., dupilumab, lebrikizumab, tralokinumab) from 5 times the half-life of each medication prior to ECD through the end of pregnancy. The cohort entry date will be matched to the date of nemolizumab dispensing, rounded down to the nearest week of gestation.

This cohort may include pregnancies among women who have dispensings or administrations of other treatments indicated for moderate to severe AD or PN (e.g., immunosuppressants, corticosteroids). Exposure to other treatments for moderate to severe AD or PN will be measured and adjustment for or stratification by use of these treatments may be considered during the analysis.

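### For AD, the index nemolizumab fill can itself satisfy the severity rule, so eligibility in the nemolizumab-versus-unexposed contrast depends on the arm and on events after cohort entry

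*Protocol*

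**What the plan says.** Section 7.3.4 of the protocol gives one rule with three alternative criteria. It applies to all cohorts and is assessed "between 12 months prior to ECD and the end of pregnancy".

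- Criterion 1: at least two "claims with an AD diagnosis code (ICD-10-CM: L20*), at least 30 days apart, from any physician", and at least one "dispensing of nemolizumab, dupilumab, abrocitinib, upadacitinib, baricitinib, tralokinumab, or lebrikizumab".
- Criterion 2: the same two codes and at least two "dispensings on different days of high potency topical corticosteroids or systemic immunosuppressants".
- Criterion 3: two AD codes from a dermatologist or allergist and at least three "dispensings on different days of medium potency topical corticosteroids, topical tacrolimus, phototherapy, or oral/parenteral corticosteroids".

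Section 7.3.6.5 requires that women in the Unexposed Cohort have no nemolizumab, dupilumab, lebrikizumab or tralokinumab "from 5 times the half-life of each medication prior to ECD through the end of pregnancy". Under section 7.3.3.1, women exposed to the listed oral JAK inhibitors "from 5 half-lives (specific for each medication) prior to ECD through the end of pregnancy will be excluded". Section 7.1 says that the final analyses will "employ a target trial emulation approach using a sequential matched cohort design".

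**The concern.** In a target trial, eligibility is settled at time zero, before assignment and without reference to it. Here the fill that defines the nemolizumab arm also supplies the drug evidence of severity. In the unexposed arm that evidence must come from other treatments, some of which may be dispensed after cohort entry. The two arms of this contrast can then differ in severity, prior treatment and contact with care because of the rule itself.

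The weights in section 7.7.3.1 target the effect in the treated, so every exposed pregnancy counts with weight 1. If some exposed women have no other qualifying treatment, the comparators needed to represent them may be scarce, and weighting cannot create them. Conditioning eligibility on events after entry is a separate selection problem, because a longer pregnancy gives an unexposed woman more time to qualify.

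**Working it through.** The plan gives no figure for this point, so the main check is a trace of who can meet which criterion.

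**Step 1: AD, Nemolizumab Cohort.** Section 7.3.6.3 counts a dispensing or dose from 95 days before ECD to the end of pregnancy. That period lies inside the 7.3.4 window. With two AD codes, the index dispensing alone meets criterion 1.

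**Step 2: AD, Unexposed Cohort.** Criterion 1 is closed during the 5-half-life period and pregnancy but open before that. Using 365 days before ECD and the 5-half-life column of Appendix D, the days in which an earlier, stopped biologic still qualifies a woman are:

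| Drug | Calculation | Days open |
|---|---|---|
| Nemolizumab | 365 − 95 | 270 |
| Dupilumab | 365 − 70 | 295 |
| Tralokinumab | 365 − 105 | 260 |
| Lebrikizumab | 365 − 123 | 242 |

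Earlier JAK inhibitor fills also qualify; Appendix D gives no half-lives for those drugs. All other unexposed AD women need criterion 2 or 3.

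**Step 3: where the asymmetry does not arise.** PN identification (7.3.5) has no drug element. The Other AD/PN Treatment Cohort (7.3.6.4) also qualifies through its own index drug, so that contrast is even-handed in this respect.

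**Step 4: case mix, on assumptions.** Let q be the share of exposed AD pregnancies that qualify only through the index fill, and k their background risk relative to the other exposed pregnancies. If weighting does not remove the difference, a null ratio reads 1 + q(k − 1). The documents give neither value. With q from 0.10 to 0.30 and k from 0.7 to 1.5:

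- lowest: 1 + 0.30 × (0.7 − 1) = 0.91
- highest: 1 + 0.30 × (1.5 − 1) = 1.15

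**Step 5: misclassified severity, on assumptions.** Section 7.3.4 cites a PPV of 76% (95% CI 53% to 90%) for a similar algorithm that did not include nemolizumab. Suppose true moderate to severe AD multiplies outcome risk by r. A null crude RR then reads (PPV_E·r + 1 − PPV_E) / (PPV_U·r + 1 − PPV_U). With PPV_E (exposed) from 0.76 to 1.0, PPV_U (unexposed) from 0.53 to 0.90 and r from 1.2 to 2.0:

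- lowest: PPV_E 0.76, PPV_U 0.90, r = 2.0: 1.76 / 1.90 = 0.93
- highest: PPV_E 1.0, PPV_U 0.53, r = 2.0: 2.00 / 1.53 = 1.31

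**Step 6: post-entry eligibility, on assumptions.** Take an unexposed woman who can qualify only by criterion 2, with high-potency fills following a Poisson process at 3 per year. Over d days the mean is m = 3d/365, and P(at least 2 fills) = 1 − e^(−m)(1 + m). Let entry be at week 6, with either a loss at week 10 or a birth at week 40.

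| Data available from | Loss at week 10 | Birth at week 40 |
|---|---|---|
| 183 days before entry | d = 183 + 28 = 211; P = 0.52 | d = 183 + 238 = 421; P = 0.86 |
| 12 months before ECD (week 2) | d = 365 + 56 = 421; P = 0.86 | d = 365 + 266 = 631; P = 0.965 |

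Use the 14% spontaneous abortion prevalence in Table 3 and let the exposed drug element be met at entry. Among admitted unexposed women the risk becomes:

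- 0.14 × 0.52 / (0.14 × 0.52 + 0.86 × 0.86) = 0.09, so a null ratio reads about 0.14 / 0.09 = 1.6
- 0.14 × 0.86 / (0.14 × 0.86 + 0.86 × 0.965) = 0.127, so a null ratio reads about 0.14 / 0.127 = 1.1

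This isolates the drug element. It ignores criterion 3, earlier biologics, and the two AD codes that both arms need and may also acquire late. It shows the mechanism and does not predict the study result.

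**The case against.** The best defence is that there is one written rule, not two. It requires two AD codes of everyone, so exposure alone qualifies nobody. That is correct, and it limits the point to how the rule operates in one contrast for one indication.

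A reader might infer that unexposed women always need two or three other dispensings. Step 2 shows otherwise: one earlier biologic or JAK inhibitor fill is enough.

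A reader might also infer that the effect in the treated is not identified for exposed women with no other qualifying treatment. The documents do not support that. Drug covariates are coded yes or no (7.4.3), treatment history looks back up to 5 years (7.4.3.5), and propensity covariates stop at cohort entry (7.7.3.1) while eligibility can be earned later. Unexposed women with no qualifying treatment before entry can therefore exist. Moreover, the US AD indication in the abstract is for use with topical therapy after inadequate control on topical prescriptions, so few on-label users may lack topical fills. Counterparts may be few, but their absence is not shown.

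Nor should unexposed admission be judged on time before pregnancy alone. At 3 fills per year, P(at least 2 fills) is 0.80 over 365 days and 0.44 over 183 days. The stated window continues through pregnancy. At term (266 days after ECD) the figures are 0.97 over 631 days and 0.88 over 449 days.

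The plan does offer partial protection: AD treatments as candidate covariates, balance, overlap and weight checks, possible adjustment for other treatments (7.3.6.5), and a bias analysis for unmeasured confounding (7.7.3.5.6). These can reveal or reduce imbalance, but none changes who is eligible. The analysis excluding systemic treatments (7.7.3.5.5) leaves the index-fill route in place.

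**Conclusion.** The point stands for AD in the nemolizumab-versus-unexposed contrast. Eligibility there depends on assignment, through the index fill, and on events after cohort entry. This conflicts with the target trial emulation claimed in section 7.1, and no planned analysis corrects it. AD is the larger indication in the protocol's own counts: Table 4 lists 7,264 pregnancies with an AD code and 207 with a PN code.

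The documents fix neither the size nor the direction of the bias. The illustrative null ratios (0.91 to 1.15 for case mix, 0.93 to 1.31 for misclassified severity, about 1.1 to 1.6 for spontaneous abortion under post-entry qualification) rest wholly on the assumptions stated with them. The first two ranges include 1. All lie below the relative risks of 2.5 and 3 that the MCM study size targets, so the concern is mainly with the interpretation of modest ratios. The study size calculation is unaffected.

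**What to change.** Add to sections 7.3.4 and 7.7.3.5 a pre-specified analysis of the unexposed contrast that establishes moderate to severe AD in both arms from information before cohort entry only, without counting the index fill. A woman would qualify with two AD codes and criterion 2, criterion 3 (with its specialist codes), or an earlier biologic or JAK inhibitor fill. The limit to pre-entry information matters: if criteria 2 and 3 still ran to the end of pregnancy, eligibility would continue to depend on post-entry events and on the arm.

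Report how many exposed pregnancies qualify only through the index fill, and how many in each cohort qualify only on post-entry data. Keep the current rule for the descriptive frequencies.

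The cost is one extra analysis and the matching text in the analysis plan. That analysis will contain fewer pregnancies, and it may drop some women whose disease is truly moderate to severe but not documented before entry. The number lost cannot be computed from the documents.

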7.3.5 Identification of PN

Pregnant women will be considered to have PN if they have at least two ICD-10-CM diagnosis codes for PN (L28.1), at least 30 days apart, between 12 months prior to pregnancy and the end of pregnancy. In a validation study, this algorithm had a PPV of 87.9% (95% CI 81.5%, 94.3%; [Roh et al., 2022](#)).

Although nemolizumab is approved for the treatment of overall PN in the US, it is authorized for the treatment of moderate to severe PN in Europe. Currently, there is not a published, validated algorithm for moderate to severe PN. Optum will continue to search the published literature over the course of the study to see if a validated claims-based algorithm for moderate to severe PN is published. If a validated algorithm is found that has suitable performance characteristics, the methods for identifying PN may be modified.

7.3.6 Study Population

7.3.6.1 Exposure Cohorts and Cohort Entry

[figure not shown]
Based on the sequential cohort design, a series of study cohorts will be established for each gestational week of pregnancy ([Caniglia et al., 2023](#); [Hernández-Diaz S et al., 2023](#)). To ensure capture of exposure to AD/PN treatments prior to the ECD but which remain in the body at ECD, the first gestational week of pregnancy will be extended (prior to ECD) by 5 times the half-life for each AD/PN treatment. For example, since nemolizumab has a half-life of 18.9 days ([Nemluvio PI, 2025](#)), the first gestational week for nemolizumab will begin 95 days (approximately 14 weeks) prior to ECD. The half-life for each AD/PN treatment is provided in [Appendix D](#).

As nemolizumab and the comparator AD/PN treatments are injection drugs that are dispensed at a pharmacy for self-injection, treatment duration will be defined as date of dispensing plus 5 times the half-life of the therapy when a single pre-filled syringe, pen, or autoinjector is dispensed. When multiple units are dispensed, the days' supply will be calculated based on the quantity dispensed and recommended administration schedule; treatment duration will be calculated as the date of dispensing plus the days' supply plus 5 times the half-life of the therapy. A treatment will be considered to be overlapping with the first gestational week of pregnancy if there is at least one dispensing or dose received during the period 5 times the half-life prior to ECD through the end of the first gestational week. At each gestational week, we will first restrict to eligible pregnancies with no administrations or dispensings of nemolizumab or the other AD/PN treatments from 5 times the half-life of the corresponding treatment (e.g., 95 days, or approximately 14 weeks, for nemolizumab) before ECD through the end of the prior gestational week. We will then classify exposure status as exposed to nemolizumab, exposed to other AD/PN treatments, or unexposed based on the pregnancy's receipt of nemolizumab or other AD/PN treatments during that gestational week. Pregnancies among women with claims for both nemolizumab and another AD/PN treatment during the relevant exposure window will be excluded. For exposed pregnancies with more than one dose of the index treatment (e.g., two doses of nemolizumab) during pregnancy, cohort entry will align with the first dose.

Cohort entry will be set at the date of dispensing in the Nemolizumab Cohort (i.e., the earliest nemolizumab administration date during a pregnancy) and the Other AD/PN Treatment Cohort,

and the corresponding day of gestation among unexposed pregnancies, rounded down to the nearest week. For example, for pregnancies entering the Week 8 Cohort, we will first select all pregnancies with no nemolizumab or other AD/PN treatment from 5 times the half-life before ECD through 7 weeks' + 6 days' gestation. Then, we will assign the pregnancies that receive nemolizumab during Week 8 (8 weeks + 0 days through 8 weeks + 6 days) to the nemolizumab-exposed group, those that received another AD/PN treatment to the other treatment-exposed group, and those that did not receive nemolizumab or another AD/PN treatment during Week 8 to the unexposed group. Cohort entry among the Week 8 nemolizumab and comparator cohorts will be set to 8 weeks' + 0 days. The pregnancies in the Week 8 exposed cohort will no longer be eligible for inclusion in subsequent weekly cohorts. However, the pregnancies in the Week 8 unexposed group will go on to be eligible for inclusion in the Week 9 Cohort, at which point their exposure status would be reassessed during Week 9 (9 weeks + 0 days through 9 weeks + 6 days). A pictorial depiction of this process can be found in Figure 1 and key pregnancy dates can be found in Table 1. If the study size does not permit weekly sequential cohorts, the cohorts may be collapsed into longer (e.g., 2-week, 4-week) intervals as needed.

Figure 1 Sequential cohort design, depicting an example of cohort entry for the Week 7 and Week 8 cohorts

Abbreviations: AD, atopic dermatitis; ECD, estimated conception date; PN, prurigo nodularis

Table 1 Pregnancy dates

Date	Definition
LMP	First day of last menstrual period 0 gestational weeks ^{0/7 days}
Gestational age	Weeks of gestation Anchored by LMP Number of completed weeks elapsed after LMP

Date	Definition
ECD	Estimated as LMP + 14 days 2 gestational weeks ^{0/7 days}
First trimester	Begins at ECD minus 5 times the half-life of the treatment Ends at LMP + 97 days
Second trimester	Begins at LMP + 98 days Ends at LMP + 195 days
Third trimester	Begins at LMP + 196 days Ends at pregnancy outcome
Pregnancy period	Begins at ECD minus 5 times the half-life of the treatment Ends at pregnancy outcome

Abbreviations: ECD, estimated conception date; LMP, first day of last menstrual period

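### Exposure classification leaves out the days' supply that the protocol itself counts in treatment duration, so some multi-unit fills before the look-back window are ignored

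*Protocol*

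**What the plan says.** Protocol 7.3.6.1 defines treatment duration in two ways. The rule for one unit is: "treatment duration will be defined as date of dispensing plus 5 times the half-life of the therapy when a single pre-filled syringe, pen, or autoinjector". For several units, "supply will be calculated based on the quantity dispensed and recommended administration schedule", and the duration is the dispensing date plus the days' "supply plus 5 times the half-life of the therapy".

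The classification rules that follow look for an event in a fixed window:

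- **Overlap with the first gestational week (7.3.6.1):** "A treatment will be considered to be overlapping with the first gestational week of pregnancy if there is at least one dispensing or dose received" from 5 half-lives before ECD to the end of that week.
- **Eligibility for each weekly cohort (7.3.6.1):** "no administrations or dispensings of nemolizumab or the other AD/PN treatments from 5 times the half-life of the corresponding treatment" before ECD to the end of the prior week.
- **Nemolizumab and Other AD/PN Treatment Cohorts (7.3.6.3, 7.3.6.4):** a dispensing or dose (7.3.6.4 also names administrations) in the same look-back or in pregnancy.
- **Unexposed Cohort (7.3.6.5):** "no dispensings or administrations of nemolizumab or the other monoclonal antibody treatments" over the same look-back and through the end of pregnancy.
- **PSUR counts (7.7.1):** the same 95-day look-back for nemolizumab.

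The stated purpose of the extended window in 7.3.6.1 is to catch drug that is still in the body at ECD.

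**The concern.** A look-back of 5 half-lives is exactly the duration the protocol gives a single unit. Applied to every fill, it treats a multi-unit fill as if all the drug were used on the dispensing day. The drugs are described as self-injected after pharmacy dispensing, and 7.4.1.1 finds nemolizumab by a product code on pharmacy claims. Later injections from the same fill are therefore not seen.

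First-trimester exposure is the window for the primary outcome, major congenital malformation (Table 2). Three groups can be misplaced:

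- A woman with a multi-unit fill just before the window and no refill meets the Unexposed Cohort definition.
- A woman who refills in pregnancy enters in the refill week, although the calculated treatment already covered ECD. Gestational week is a matching variable.
- A woman who switches drug escapes the dual-exposure exclusion (7.3.3.2), because her earlier fill lies outside the window.

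The sensitivity analyses in 7.7.3.5.4 shorten the window, drop pre-conception fills, or require two or more dispensings. None extends the look-back by days' supply.

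**Working it through.** **Inputs from the protocol.** Nemolizumab half-life 18.9 days (7.3.6.1). Five-half-life windows *W* (Appendix D): dupilumab 70 days, nemolizumab 95, tralokinumab 105, lebrikizumab 123. ECD = LMP+14 and the first trimester ends at LMP+97 (Table 1).

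**Assumption.** The protocol gives no days' supply *S*. I use 28, 56 and 84 days, each dispensed as more than one unit.

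**The plan's own figure.** 5 × 18.9 = 94.5, rounded up to 95 days. This reproduces.

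**Gap.** For a fill *t* days before ECD:

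- by the duration formula, treatment reaches ECD when *t* ≤ *S* + *W*;
- by the cohort rules, the fill counts only when *t* ≤ *W*.

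Fills from *W*+1 to *W*+*S* days before ECD are treatment by the first rule and nothing by the second. For nemolizumab these are days 96 to 123, 151 or 179.

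**Fill one day outside the window.** Duration ends at -(*W*+1) + *S* + *W* = *S* - 1 days after ECD, for all four drugs:

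| *S* | Duration ends | Nemolizumab supply ends (filled ECD-96) | Dupilumab supply ends (filled ECD-71) |
|---|---|---|---|
| 28 | ECD+27 | ECD-68 | ECD-43 |
| 56 | ECD+55 | ECD-40 | ECD-15 |
| 84 | ECD+83 | ECD-12 | ECD+13 |

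ECD+83 is LMP+97, the last day of the first trimester. For a single unit at ECD-96, duration ends at -96 + 95 = ECD-1, so there is no gap.

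**Regular refillers, primary window.** If fills are spread evenly relative to ECD, the chance of no fill in the window plus the first week is (*S* - (*W*+7))/*S*, or zero if negative.

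- *S* = 84: nemolizumab 84 - 102 < 0, so 0%; tralokinumab (112) and lebrikizumab (130) also 0%; dupilumab (84 - 77)/84 = 7/84 = 8%.
- *S* = 56: 0% for all four.

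**Regular refillers, 1.5-half-life sensitivity window for nemolizumab.** 29 + 7 = 36 days: (84 - 36)/84 = 57%; (56 - 36)/56 = 36%.

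**Dilution.** If a share *c* of the unexposed group in fact carries the nemolizumab risk, observed RR = RR/(1 + *c*(RR - 1)). At RR = 2.5 (a Table 3 value) and assumed *c* of 1%, 3% and 10%: 2.5/1.015 = 2.46, 2.5/1.045 = 2.39, 2.5/1.15 = 2.17.

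**The case against.** The text does not say dispensing date alone. The overlap rule and 7.3.6.3 and 7.3.6.4 say dispensing or dose, and doses projected from the days' supply may be what was meant. This stands as a point about wording. It does not remove the problem: no projection rule is given, and 7.3.6.5 speaks only of dispensings or administrations. Under that reading one pregnancy could satisfy both the Nemolizumab and the Unexposed definitions.

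A reader might infer that women under treatment at conception are commonly counted as unexposed. The documents do not support that for nemolizumab. Supply still running at ECD would need more than 95 days in one fill, and in the primary window regular refillers on 84-day or shorter fills are all caught. The 57% and 36% belong only to the 1.5-half-life sensitivity analysis. Even there, a woman still refilling every 84 days fills again by ECD-30 + 84 = ECD+54, so she enters late and does not stay unexposed.

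A reader might also infer bias to the null throughout. That is too broad. The active-comparator contrast does not use the unexposed group and is touched only through switchers and late entry. Former dupilumab users among the unexposed pull the nemolizumab estimate to the null only if dupilumab shares the effect.

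Finally, whether a woman who refills in Week 6 can first serve as unexposed in Weeks 2-5 is itself unsettled. The Week 8 example in 7.3.6.1 lets an unexposed pregnancy move on to be reassessed, while 7.3.6.5 requires no dispensing to the end of pregnancy.

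**Conclusion.** The inconsistency is real. The protocol defines a duration for multi-unit fills and then applies rules that ignore it, so some pregnancies with treatment ongoing at ECD by its own formula are classed as unexposed or entered late. This is a rule that gives the wrong result, not detail left for the SAP.

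In the primary analysis the effect falls mainly on women who stopped before the window or refilled late. It dilutes the nemolizumab-versus-unexposed contrast where the earlier drug was nemolizumab; on the assumed shares of 1% to 10%, an RR of 2.5 would read 2.46 to 2.17. The actual share depends on how many fills contain several units, which the protocol does not give, so material bias is possible but not shown. The dates rest on assumed supplies of 28 to 84 days. No sample-size figure changes.

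**What to change.** In 7.3.6.1 and 7.3.6.3 to 7.3.6.5, the weekly washout, the dual-exposure exclusion (7.3.3.2) and the PSUR counts (7.7.1), count a multi-unit fill as exposure when its calculated treatment duration reaches ECD. This is the same as its days' supply extending into the 5-half-life window (*t* ≤ *S* + *W* means -*t* + *S* ≥ -*W*), so the 95-day research question is unchanged.

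- Assign such pregnancies to the first (extended) gestational-week cohort. At minimum, bar them from the Unexposed Cohort.
- In 7.7.3.5.4 use days' supply plus 3 or 1.5 half-lives for multi-unit fills, and keep the dispensing-date rule as a sensitivity analysis.
- Reconcile the Week 8 example in 7.3.6.1 with 7.3.6.5 on pregnancies exposed later.

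Days of supply are already in the pharmacy claims (7.2.1), so most of this is wording and programming. There are two costs. Days' supply is recorded with error. The look-back also lengthens: at 84 days it is 154 days for dupilumab, 179 for nemolizumab, 189 for tralokinumab and 207 for lebrikizumab. The last two exceed the 183 days of enrolment required before cohort entry (7.3.2, 7.3.6.6) for an entry at ECD. In linked claims-EHR data, pharmacy coverage is required only for the pregnancy period, which starts 5 half-lives before ECD (7.3.2, Table 1). Either apply the rule to all pharmacy data available, and say that earlier fills may be missed, or lengthen the required pharmacy coverage and accept some loss of pregnancies.

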7.3.6.3 Nemolizumab Cohort

The Nemolizumab Cohort will include all pregnancies among women with moderate to severe AD or PN and at least one dispensing or dose of nemolizumab from 95 days (approximately 14 weeks) prior to ECD through the end of pregnancy. Cohort entry will be set at the date of the first nemolizumab dispensing, rounded down to the nearest week of gestation.

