7.3.6.7 Follow-up

For each weekly cohort, pregnancies will be followed from the date after cohort entry until the earliest of the end of pregnancy, disenrollment from the health plan (for claims databases), 8 weeks with no clinical activity recorded (for the linked claims-EHR database or EHR-only databases) or the end of the study period (31 March 2032 or latest data available). Each linked infant will be followed from delivery until the earliest of end of first year of life, disenrollment from the health plan (for claims databases), 8 weeks with no clinical activity recorded (for the linked claims-EHR database or EHR-only databases) or the end of the study period. Follow-up for spontaneous abortion and elective termination will be censored at 20 weeks' gestation, and follow-up for preterm birth will be censored at 37 weeks' gestation. The censoring events for each outcome are summarized in [Table 2](#).

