7.7.3 Final Analysis

For the final study report, Optum will match nemolizumab-exposed pregnancies to the two comparator groups (Other AD/PN Treatment Cohort and Unexposed Cohort) in a 1:4 ratio based on maternal age at cohort entry, gestational week of dispensing, indication, and calendar week, separately within each data source. If the study size does not permit matching in these categories (or intervals), the sequential cohorts may be collapsed to 2-week intervals for gestational week at cohort entry or wider categories for maternal age at cohort entry and calendar time. A variable matching ratio of 1:up to 4 may also be considered.

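### Weekly cohort entry is set before exposure is known, giving exposed pregnancies up to 6 guaranteed event-free days against the Unexposed Cohort; the entry date for collapsed cohorts is not stated

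*Protocol*

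**What the plan says.** Section 7.3.6.1 forms one cohort per gestational week.

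- **Exposure.** The example assigns pregnancies treated "during Week 8 (8 weeks + 0 days through 8 weeks + 6 days) to the nemolizumab-exposed group", and "those that did not receive nemolizumab or another AD/PN treatment during Week 8 to the unexposed group". A pregnancy does not have to be ongoing at the end of the week to count as unexposed.
- **Entry.** "Cohort entry among the Week 8 nemolizumab and comparator cohorts will be set to 8 weeks" and 0 days. For nemolizumab, Section 7.3.6.3 repeats the rule: "Cohort entry will be set at the date of the first nemolizumab dispensing, rounded down to the nearest week of gestation". Comparators take the same floor: "and the corresponding day of gestation among unexposed pregnancies, rounded down to the nearest week".
- **Follow-up.** Section 7.3.6.7 says that "pregnancies will be followed from the date after cohort entry until the earliest of the end of pregnancy". Table 2 starts follow-up at cohort entry for ectopic pregnancy, elective termination and spontaneous abortion. It starts at the later of entry or 20 weeks for live birth, preterm birth and stillbirth, and at delivery for MCM and SGA.
- **Collapsing.** Section 7.3.6.1 adds that "the cohorts may be collapsed into longer (e.g., 2-week, 4-week) intervals as needed". Section 7.7.3 says only that "the sequential cohorts may be collapsed to 2-week intervals for gestational week at cohort entry". Neither gives the entry date of a collapsed cohort.

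**The concern.** In a target trial emulation, which Section 7.1 says this is, eligibility, assignment and time zero should coincide. Here assignment can fall up to 6 days after time zero.

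Take two pregnancies at 8 weeks + 0 days. One is dispensed nemolizumab on 8 weeks + 5 days. It had to be ongoing that day, so its first five days at risk are event-free by construction. The other is lost on 8 weeks + 2 days without a dispensing, and becomes an event in the unexposed group. Events early in the interval can only accumulate on the unexposed side until dispensings occur.

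The direction matters: in a safety study, a drug with no effect looks protective and a modest harm is partly hidden. Aligning entry by week removes immortal time between weeks, not within a week. None of the sensitivity analyses in Section 7.7.3.5 addresses it.

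**Working it through.** **The plan's own figure.** The protocol gives no count of guaranteed days. The input used below is the 14% spontaneous abortion risk in Table 3. To confirm that it is the comparator risk, I reproduced the Table 3 figure for RR 2, with p1 = 0.28, p0 = 0.14, ratio r = 4, two-sided alpha 0.05 and 80% power:

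- pooled p = (0.28 + 4 × 0.14)/5 = 0.168
- n = [1.960 × √(5 × 0.168 × 0.832) + 0.842 × √(4 × 0.28 × 0.72 + 0.14 × 0.86)]² / (4 × 0.14²) = (1.639 + 0.810)² / 0.0784 ≈ 76.5, rounded up to 77. Table 3 states 77.

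**Guaranteed days.** An interval of L days with entry on its first day gives dispensing offsets 0 to L − 1. The maximum is L − 1 and, if dispensing is uniform, the mean is (L − 1)/2. Starting follow-up the day after entry can shift the count by one day.

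| Interval | Entry date stated? | Maximum | Mean |
|---|---|---|---|
| 1 week | yes | 6 | 3.0 |
| 2 weeks | no; assumes start of block | 13 | 6.5 |
| 4 weeks | no; assumes start of block | 27 | 13.5 |

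**Illustrative size by hand (Week 8 entry, no true effect, constant hazard).**

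- Cumulative hazard from week 2 to week 20 (126 days): −ln(0.86) = 0.1508, or 0.001197 per day.
- Unexposed, 84 days from 8w+0d to 20w+0d: 1 − exp(−84 × 0.001197) = 0.0957.
- Exposed, on average 3 fewer days truly at risk: 1 − exp(−81 × 0.001197) = 0.0924.
- Risk ratio 0.0924/0.0957 = 0.966. The hazard ratio is roughly 81/84 = 0.96.

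**Cox hazard ratio.** Solving the expected Cox score equation with 1:4 allocation, uniform dispensing and rare exposure gives, at Week 8 entry:

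| Assumed hazard shape | Weekly | 2-week* | 4-week* |
|---|---|---|---|
| Constant | 0.96 | 0.92 | 0.83 |
| Halving every 6 weeks | 0.94 | 0.86 | 0.74 |
| Halving every 3 weeks | 0.90 | 0.80 | 0.64 |

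*Only if entry is the start of the collapsed interval.

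Over entry at Weeks 4, 8 and 12 and all three shapes, the weekly range is 0.89 to 0.97. The hazard shapes and uniform dispensing are assumptions; the protocol gives neither.

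**Dilution in the pooled estimate.** Dispensings from 95 days before ECD feed the first cohort. If those pregnancies enter at Week 2, as Table 2 lists, the dispensing precedes time zero and adds no guaranteed time. The protocol does not give the share entering later. If it were 25% to 50%, a simple average without event weighting would run from 0.75 × 1 + 0.25 × 0.96 = 0.99 to 0.50 × 1 + 0.50 × 0.90 = 0.95 for weekly cohorts.

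**After the change.** With time zero on the dispensing day, and comparators ongoing and untreated on that same gestational day, guaranteed time is 0 days and the null hazard ratio is 1.00 at any interval width.

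**The case against.** The case for leaving the design alone has four parts.

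1. **The bias is small in the design as planned.** With weekly cohorts the guaranteed time averages 3 days, and pregnancies entering at Week 2 through earlier dispensing dilute it. This stands. The weekly effect is modest, but it has one direction and nothing in the protocol removes it.

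2. **It misses the primary outcome.** MCM and SGA follow-up starts at delivery, and study size is set on MCM. The Other AD/PN Treatment Cohort is rounded in the same way and matched on gestational week, so that contrast is roughly symmetric. Live birth, preterm birth and stillbirth are touched only in cohorts entering from about 20 weeks. All of this stands. What remains is three outcomes in one of the two contrasts, though each is a named objective with a planned hazard ratio.

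3. **Four-week figures are not the protocol's.** A reader might infer that guaranteed time grows to 27 days. The protocol does not say so. Its stated rule floors entry to the nearest week, and if that is kept while only the cohort or matching band widens, the maximum stays at 6 days. Section 7.7.3 also names only 2-week collapsing for gestational week. What stands against the protocol is that it allows collapsing without fixing the entry date. Collapsing is plausible: Table 4 shows only 209 AD-coded pregnancies with a dupilumab dispensing in the ORD from 2020 to a partial 2024, and matching is done separately within each data source.

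4. **A landmark at the end of the interval is not a free remedy.** Correct; see the fix.

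**Conclusion.** The misalignment is real and follows from the protocol's own wording. For pregnancies first dispensed after conception, weekly cohorts carry up to 6 days (mean about 3) of guaranteed event-free time. This biases the hazard ratios for spontaneous abortion, ectopic pregnancy and elective termination against the Unexposed Cohort towards protection. For spontaneous abortion at Week 8 entry, the null hazard ratio is about 0.90 to 0.96, given a 14% risk, uniform dispensing and the assumed hazard shapes. These are not predictions of the study's pooled hazard ratio, which would lie closer to 1.

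If intervals were collapsed and entry set at the start of the block, the maximum would be 13 or 27 days and the same illustration would give about 0.8 to 0.9 or 0.6 to 0.8. That outcome is conditional on an entry rule the protocol does not state. Nor do the documents support extending the bias to MCM, SGA or the active-comparator contrast. The point should be corrected before the final analysis, but it does not undermine the primary objective.

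**What to change.** **Change.** In Sections 7.3.6.1, 7.3.6.3 to 7.3.6.5 and 7.3.6.7:

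- set time zero for each exposed pregnancy at the actual gestational day of dispensing or administration;
- give each matched comparator that same gestational day, and require it to be ongoing and untreated on that day;
- state that this applies at any interval width;
- reconcile Sections 7.3.6.1 and 7.7.3 on which widths are permitted.

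**Cost.** Slightly more matching work, and reliance on day-level gestational dating. Section 7.2.1.1.2 reports a median difference of 4.0 days between code-based and adjudicated LMP. Data extraction for the final report is planned from December 2032, so there is time.

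**Alternative.** Starting follow-up in every arm after the exposure-defining interval, among ongoing pregnancies, also removes the guaranteed time. But Table 2 would need revision: the Week 19 cohort would start at 20 weeks + 0 days, the censoring date for spontaneous abortion and elective termination, and the Week 36 cohort at 37 weeks + 0 days, the censoring date for preterm birth. Both would have no follow-up. Events inside the interval, including early losses after dispensing, would also be dropped, and more of them as the interval widens. The same-day rule is therefore preferable.
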